Study Protocol

Official Title: Consensus-based algorithms to address opioid misuse behaviors among individuals prescribed long-term opioid therapy: developing implementation strategies and pilot testing

PI: [name], PhD

Study Coordinator: [name], BS

ClinicalTrials.gov ID (NCT number): NCT05182606

Protocol Date: May 29, 2025

Scientific Background

Long-term opioid therapy (LTOT) remains a common treatment for chronic pain, despite growing awareness of its associated risks. Although recent data from the Centers for Disease Control and Prevention (CDC) shows a reduction in opioid prescribing, an estimated 19 million opioid prescriptions are still written each month. In 2017, clinicians wrote 58.5 opioid prescriptions per 100 persons nationally, and 57.6 per 100 in Allegheny County, highlighting the ongoing relevance of opioid prescribing both locally and nationally. Primary care providers (PCPs), who prescribe more opioids than any other specialty, face significant challenges in managing the care of patients on LTOT, including opioid misuse behaviors.

Opioid misuse behaviors, or concerning behaviors, are extremely common among patients on LTOT. These behaviors include missing appointments, using more opioid medication than prescribed, and illicit substance use, with some studies estimating that up to 85% of LTOT patients exhibit such behaviors. Managing these behaviors is crucial as they may lead to opioid use disorder (OUD) and other negative outcomes. However, existing guidelines, including the 2016 CDC Guideline for Prescribing Opioids for Chronic Pain, do not provide clear recommendations on how to address these behaviors when they arise. As a result, the responsibility often falls to PCPs, who may lack the necessary tools to effectively manage these complex situations.

To address this gap in knowledge and practice, we used a Delphi approach to identify the most common and challenging concerning behaviors and develop consensus-based management algorithms. These algorithms provide structured guidance for PCPs, helping them adopt best practices in managing LTOT patients with concerning behaviors. Our preliminary data from a rigorous 4-round Delphi study, which included pain experts, established consensus on these behaviors and management strategies. If successful, these algorithms will ultimately serve as essential tools for PCPs, accelerating the research-to-practice pipeline and improving the management of LTOT patients, with the potential to reduce opioid misuse-related harms and mitigate the impact of the opioid epidemic. This project is supported by the NIH Helping to End Addiction Long-term (HEAL) initiative, aligning it with national efforts to address the opioid crisis. If successful, these algorithms will ultimately serve as essential tools for PCPs, accelerating the research-to-practice pipeline and improving the management of LTOT patients, with the potential to reduce opioid misuse-related harms and mitigate the impact of the opioid epidemic.

Study Objectives

Aim 1

To a) identify and b) operationalize implementation strategies for the algorithms. Our approach will be guided by the Consolidated Framework for Implementation Research (CFIR) and the Expert Recommendations for Implementing Change (ERIC). Optimal implementation strategies will be uncovered through primary care provider experiences with Standardized Patients (SPs) followed by CFIR- and ERIC-guided group interviews. Using our prior expertise developing clinic-wide opioid risk reduction strategies and a Patient-Provider advisory board, we will

develop a comprehensive implementation package that can be delivered to primary care practices.

Aim 2

To conduct a pilot trial of the algorithms. Guided by the CFIR-based implementation plan and using the implementation package developed in Aim 1b, we will conduct a pilot trial to investigate the algorithms' feasibility, acceptability, and preliminary effectiveness.

Integrate algorithms into the EHR

To develop, evaluate, and test a risk score for the presence of opioid misuse behavior from documentation in the electronic health record including structured data such as encounters, diagnoses and prescriptions, and incorporating unstructured, free-text clinical documentation. The resulting risk score will be used as an outcome measure in the pilot study.

Study Design & Methods

Aim 1

We will conduct several study sessions involving 2 Standardized Patients (SPs), each portraying different cases, who will be seen by 2 primary care providers (PCPs) per session. SPs are healthy individuals trained to consistently and reproducibly portray patients in medical or communication-based scenarios. Each encounter will simulate a patient-PCP appointment in which the PCP must address opioid misuse behaviors exhibited by the SP. To ensure consistency across sessions and facilitate productive group interviews, each session will feature the same 2 SPs. The sessions will last five hours, including a half-hour orientation, three consecutive hour-long SP encounters, an hour-long group interview, and short breaks. These sessions will be conducted virtually via Zoom.

At the beginning of each session, PCP participants will be consented, enrolled in the study, and will complete a demographic and practice characteristics survey, along with questions about their knowledge and attitudes toward treating chronic pain and addiction. The surveys will be adapted from previous work and conducted via REDCap. During the study, PCPs will use the algorithms provided to create treatment plans for managing the concerning behaviors exhibited by the SPs. Each case will focus on one branch of an algorithm, but PCPs will have access to laminated cards (sent via email) containing all algorithms to simulate real-world decision-making.

Study staff will facilitate the Zoom sessions, utilizing breakout rooms for the SP encounters. PCPs will have 15 minutes to review patient information, such as urine drug tests and prescription monitoring data, and evaluate the patient. They will see patients longitudinally up to 3 times, with 5-minute intervals between each visit to write orders for lab tests, referrals, and medications, and complete a brief electronic survey. The longitudinal case will take

approximately 60 minutes in total. After each SP encounter, PCPs will participate in a structured group interview to discuss the session.

Aim 2

We will conduct a pilot trial at 3 UPMC sites: 2 UPMC CMI community primary care practices and 1 UPMC Presbyterian practice, to assess the feasibility, acceptability, and preliminary effectiveness of the algorithms. All PCPs at each site will participate. The pilot trial aims to mimic key elements of the future effectiveness-implementation hybrid trial, including PCP recruitment and consent, PCP orientation to the algorithms, and outcome assessment. The intervention will be implemented at the pilot sites for 6 months or longer, depending on the clinic's discretion.

A survey will be administered to PCPs to assess algorithm use, asking which algorithms were used, how often, and any resulting changes in outcomes, such as opioid dose reduction. The primary feasibility benchmark will be that 80% of PCPs report using at least one algorithm during the study period. Feasibility and acceptability will also be assessed qualitatively through interviews with the PCPs.

In addition to the study sessions, algorithm integration into the Electronic Health Record (EHR) will be developed through the Electronic Health Record Research Request (R3). For the development of an opioid misuse risk score, we will conduct a retrospective analysis of EHR data, including structured and primary care textual documentation, for patients engaged in primary care at the practices enrolled in the overall study. This analysis will include clinical records of all patients prescribed chronic opioid therapy. We will extract both structured and textual data from the EHR and identify patients who developed opioid use disorder (OUD) using encounter diagnoses. Additionally, patients with documented evidence of opioid misuse behavior will be identified through clinician chart review.

To develop the risk score, we will apply machine learning techniques to identify over-represented terms, phrases, and concepts in the textual documentation of patients who developed OUD or exhibited opioid misuse behaviors. The structured and scored textual data will then be fed into further machine learning algorithms to create a risk score specifically tailored for the practices participating in the study. This risk score for opioid misuse and OUD will then be used as an outcome measure in the pilot study of the consensus-based algorithm to address opioid misuse behaviors.

To improve the model, we may use a sample of notes from patients identified with opioid misuse behaviors, which will be de-identified by an honest broker before integration into the training data set for the machine learning model.

After completing Aim 1, we will pilot an implementation strategy bundle for the algorithms in three clinics. The pilots will be staggered, so they do not all begin simultaneously. Each pilot will last six months, and the clinics will maintain access to some materials, such as the website, even after the pilot period is complete.

Inclusion Criteria

Aim 1:

Primary care providers at UPMC practices
18 years+

Aim 2:

-Providers from the 4 identified pilot sites for Aim 2
-Patients from the 4 identified pilot sites who are on long-term opioid therapy (LTOT)
-18 years+

Exclusion Criteria

Aim 1:

Non-UPMC affiliates, trainees (residents and fellows), those with < 2 years of experience, and PCPs from the practices identified as pilot sites in Aim 2

Aim 1 and Aim 2:

Children under 18 years of age

Statistical Analysis Plan

Aim 1: As 2 SP cases will be presented per session, 12 SP sessions will be required to present all 23 cases. Group interviews will be analyzed using thematic analysis. There may be cases that we would like to revisit, either because we did not receive sufficient feedback or because feedback from subsequent cases makes it useful to revisit an earlier case.

Aim 2: For EPIC tool usage report, analysis will be conducted in the following way:

- Monitoring the number of total encounters within the past 2 weeks
- For sub-group analysis: exclude people with 32 or fewer encounters per week
- For these encounters, obtain data on use of Epic tools designed for the study, which are documentation tools and decision and ordering support
- Analyses will be conducted by provider but de-identified

Analysis for Aim 2 will be conducted using descriptive statistics and pre/post analysis. The effectiveness of the implementation strategy bundle will be analyzed using t-tests to compare outcomes at pre- and post-intervention with baseline values.

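### The misuse risk score used as a pilot outcome takes prescriptions as an input, so it can change because prescribing changed, and the pre/post comparison cannot tell this from a change in misuse

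*Combined protocol and SAP*

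**What the plan says.** Under Study Objectives (Integrate algorithms into the EHR), the risk score for misuse is to draw on documentation "including structured data such as encounters, diagnoses and prescriptions", together with free-text notes. The same paragraph gives its purpose: "The resulting risk score will be used as an outcome measure in the pilot study".

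Study Design & Methods, Aim 2, describes the construction: "The structured and scored textual data will then be fed into further machine learning algorithms to create a risk score". The training cases are patients with an OUD encounter diagnosis, together with others for whom "patients with documented evidence of opioid misuse behavior will be identified through clinician chart review". No final feature list, weights or look-back window is given.

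The same section describes a survey of PCPs about their use of the algorithms and "any resulting changes in outcomes, such as opioid dose reduction". The Statistical Analysis Plan, Aim 2, adds that the study's Epic tools are "documentation tools and decision and ordering support".

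The analysis of effectiveness in the Statistical Analysis Plan is descriptive statistics plus pre/post t-tests. No concurrent control is described, and the risk score is not mentioned there by name.

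**The concern.** Prescriptions are in two places at once: among the things the intervention may change, and among the inputs to the outcome that is meant to show whether misuse changed.

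The model is fitted to retrospective records, so any weight on prescriptions reflects how prescribing and misuse went together before the algorithms were in use. Once PCPs change prescribing because an algorithm prompts it, that learned relation need not hold. A score can predict misuse well in the training records and still be a poor measure of change in misuse under an intervention that acts on its inputs.

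At stake is the pilot's statement on preliminary effectiveness. A fall in the score might partly restate a reduction in prescribing. The pilot is also meant to rehearse outcome assessment for the later hybrid trial, so an unexamined score could be carried forward.

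**Working it through.** There is no stated figure to reproduce. The documents give no sample size, alpha, effect size or standard deviation for the score. The check has a documentary part and an illustration under assumed values.

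**Documentary chain**

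1. Prescriptions are a named input (Integrate algorithms into the EHR).
2. The score is a pilot outcome (same section, and again under Study Design & Methods, Aim 2).
3. The plan foresees that algorithm use may change opioid dose (Aim 2, PCP survey), and the pilot provides ordering support (Statistical Analysis Plan, Aim 2).
4. The comparison is pre/post with no described control (Statistical Analysis Plan, Aim 2).
5. Nothing in the documents excludes or freezes inputs that the intervention can alter, checks how the score responds to change, or names a second patient-level misuse measure.

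Steps 1 to 3 give a route by which the score can move without misuse moving. Steps 4 and 5 mean that the analysis would not detect it. The route is open only if the model weights prescriptions and prescribing does shift.

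**Illustration 1: one patient's score.** Assume a logistic score that starts at 0.30, and a change in prescription inputs that lowers the log-odds by d. The new score is expit(logit(0.30) − d), with logit(0.30) = −0.847.

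- d = 0.10: 0.279, a relative fall of 7%
- d = 0.25: 0.250, a relative fall of 17%
- d = 0.50: 0.206, a relative fall of 31%

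The logistic form, the starting score and every d are assumptions. If the weight had the opposite sign, the score would rise.

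**Illustration 2: the t-test.** Assume no true change in misuse, a two-sided paired test at 0.05 (normal approximation) and a pre/post correlation r = 0.5. Let w be the score SDs per SD of the prescription input, and s the shift in that input in SDs. Then

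d = w·s / √(2(1 − r)), and P(reject) = Φ(d√n − 1.96) + Φ(−d√n − 1.96).

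With r = 0.5 the denominator is 1, so d = w·s. For w = 0.3, s = 0.5 and n = 200: d = 0.15, d√n = 2.12, and P = Φ(0.16) plus a negligible second term = 56.4%.

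| w | s | n = 50 | n = 200 | n = 400 |
|---|---|---|---|---|
| 0 | any | 5% | 5% | 5% |
| 0.1 | 0.2 | 5.2% | 5.9% | 6.9% |
| 0.3 | 0.2 | 7.1% | 13.6% | 22.4% |
| 0.3 | 0.5 | 18.6% | 56.4% | 85.1% |
| 0.5 | 0.5 | 42.4% | 94.2% | 99.9% |

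The chance of a significant score change with misuse unchanged runs from the nominal 5% to near certainty. All of w, s, r and n are assumed. The table shows that the answer turns on quantities the plan does not give; it does not estimate the distortion in this trial.

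**The case against.** The strongest reply is that everything depends on a model not yet described. Inputs are listed as examples, the weights may be negligible, and opposing shifts may cancel. The score is one outcome in a pilot whose stated primary benchmark is PCP-reported use of the algorithms, and no rule says how a score change will be interpreted. All of this stands. It limits the claim to what can happen, but it does not close the route or supply a check.

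A reader might infer stronger points that the documents do not support:

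- **That the score must move whenever an algorithm is followed.** This needs non-zero weights and an actual shift in inputs. Neither is documented.
- **That encounters are a second contaminated input, because closer follow-up adds visits.** Nothing says that visit counts will change in the pilot. The repeat visits, and the intervals in which PCPs are "to write orders for lab tests, referrals, and medications", belong to the Aim 1 simulation with standardized patients. Scientific Background also counts missed appointments among the concerning behaviors, so encounter data may carry the very signal that is wanted.
- **That dose reduction is already a separate outcome.** It appears only as an example in a PCP survey, not as a specified patient-level endpoint.
- **That the planned score should be replaced by one without these inputs.** That would lean more heavily on diagnoses and note text, and the pilot introduces its own documentation tools. Prescription data may also carry some real misuse signal. A sensitivity analysis avoids forcing that trade.

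**Conclusion.** The concern holds in a limited form. Prescriptions are a named input, prescribing is something the plan expects algorithm use may change, and an uncontrolled pre/post t-test cannot tell changed prescribing from changed misuse. A score change on its own therefore should not be read as a change in misuse.

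The size and direction cannot be determined from the documents. Under the assumed values above, the effect ranges from none to large. The conclusion does not need any particular value in that range. It needs only that the model may weight prescriptions and that no safeguard is described. A reader might go further and call the outcome uninterpretable, but without the features and weights the documents do not support that. This is an inexpensive improvement to the analysis plan, not a reason to drop the score.

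**What to change.** Keep the planned score as the pilot outcome and add the following to the Statistical Analysis Plan, Aim 2, before the pilot data are analyzed:

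- A pre-specified sensitivity analysis reporting the pre/post change in the score with opioid prescription and dose inputs held at each patient's values from before that clinic's go-live, or, alternatively, from a refit without those inputs.
- Missed appointments and other recorded-behavior inputs retained in that analysis.
- Opioid dose change from the record reported on its own line.
- A rule of interpretation: attribute a score change to misuse only if it persists in the sensitivity analysis. Persistence is necessary but not sufficient, since there is still no control. A change that disappears is unattributed rather than proven an artefact, because prescription data may hold some misuse signal.

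The cost is one extra model run and one table line, with no new data. If the refit is used, the score may discriminate less well, by an amount that cannot be stated in advance. The analysis leaves untouched any effect of the study's documentation tools on the free text that the score reads; that needs separate handling.

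### Nothing keeps a patient's own training data out of that patient's outcome score, so misuse-positive patients can show a false fall in the risk score

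*Combined protocol and SAP*

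**What the plan says.** Under Study Objectives (Integrate algorithms into the EHR) the plan sets out to build, evaluate and test a score for opioid misuse from the health record, and adds: "The resulting risk score will be used as an outcome measure in the pilot study".

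Study Design & Methods, Aim 2, describes how the score is built:

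- **Patients.** The data are retrospective records "for patients engaged in primary care at the practices enrolled in the overall study". On extent: "This analysis will include clinical records of all patients prescribed chronic opioid therapy".
- **Labels.** Opioid use disorder is taken from encounter diagnoses. In addition, "patients with documented evidence of opioid misuse behavior will be identified through clinician chart review".
- **Features.** Machine learning will "identify over-represented terms, phrases, and concepts in the textual documentation of patients who developed OUD or exhibited opioid misuse behaviors". These text features and the structured data then go into further algorithms to "create a risk score specifically tailored for the practices participating in the study".
- **Optional enrichment.** Extra notes from patients with misuse behaviours, de-identified by an honest broker, may be added to the training set.

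Inclusion Criteria, Aim 2, defines pilot patients as adults on long-term opioid therapy (LTOT) at the pilot sites. Statistical Analysis Plan, Aim 2, calls for descriptive statistics and "t-tests to compare outcomes at pre- and post-intervention with baseline values".

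None of these sections gives a hold-out sample, cross-fitting, a training window, a model-lock date or a rule for scoring pilot patients.

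**The concern.** Taken together, these sections make the training patients and the outcome patients overlap. A model fitted to a patient's own notes and label tends to score that patient too high if the label is positive and too low if it is negative. New notes from the same patient do not carry that fitted-in error.

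If baseline scores come from the training records and follow-up scores from later records, the two are not comparable. Positives can drift down and negatives up although nobody's behaviour has changed. Choosing terms by their association with the label adds to the effect, because that step also uses the patient's own label.

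The algorithms are aimed at patients with concerning behaviours, so the spurious improvement would appear in the group of most interest. The pilot is also meant to rehearse outcome assessment for a later hybrid trial, so a faulty scoring rule could be carried forward.

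**Working it through.** **1. What the documents supply.** They give the overlap of populations, label-driven feature selection, a six-month pilot per clinic and pre/post t-tests. They give no patient number, feature count, model type, alpha or performance figure for the score. There is no stated figure to reproduce, so the size must be simulated under assumptions.

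**2. Set-up, with true change fixed at zero.** All of the following is assumed.

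- Each feature is a stable part with variance r plus fresh noise with variance 1 - r at each visit, so r is the between-visit correlation.
- Five features are informative (coefficient 0.5). The label depends only on the stable part, so ordinary regression to the mean is absent by construction.
- Score: s = 1/(1 + exp(-(b0 + x·b))), fitted by ridge logistic regression with penalty λ to baseline features and labels.
- Change: d = s(follow-up) - s(baseline), tested by a two-sided t-test at 0.05.
- Comparison: 5-fold patient-level cross-fitting, with each patient scored at both visits by the same model trained on the other folds.
- There are 40 runs per row, so rejection rates carry a simulation error of about 3 to 8 points.

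**3. Results.** Prevalence of positives is 30% except where marked.

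| N | Features | λ | r | In-sample: positives | In-sample: negatives | In-sample: all | Rejected, positives | Cross-fit: positives |
|---|---|---|---|---|---|---|---|---|
| 300 | 100 | 10 | 0.5 | -0.101 | +0.047 | +0.003 | 98% | 0.000 |
| 300 | 100 | 100 | 0.5 | -0.042 | +0.017 | -0.001 | 95% | 0.000 |
| 300 | 100 | 10 | 0.8 | -0.050 | +0.019 | -0.001 | 63% | -0.006 |
| 1000 | 100 | 10 | 0.5 | -0.033 | +0.016 | +0.001 | 83% | 0.000 |
| 1000 | 100 | 10 | 0.8 | -0.015 | +0.007 | 0.000 | 40% | -0.001 |
| 3000 | 100 | 10 | 0.5 | -0.012 | +0.005 | 0.000 | 65% | 0.000 |
| 3000 | 100 | 10 | 0.8 | -0.004 | +0.002 | 0.000 | 20% | 0.000 |
| 300 | 10 | 1 | 0.5 | -0.009 | +0.007 | +0.002 | 13% | +0.002 |
| 1000 | 10 | 1 | 0.8 | 0.000 | +0.002 | +0.001 | 8% | +0.002 |
| 300 (10% positive) | 100 | 10 | 0.8 | -0.080 | +0.012 | +0.002 | 70% | -0.003 |

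With features identical at both visits (r = 1), every change was 0.000.

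**4. Why the overall mean hardly moves.** The two drifts offset each other. In the first row, 0.30 × (-0.101) + 0.70 × 0.047 = -0.0303 + 0.0329 = +0.0026, which matches the tabulated +0.003.

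**5. Wider assumptions, still with no true change.**

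- 500-1000 patients, 200-500 features (10 informative), about 30% positive: false falls of 0.10 to 0.20 in positives. Out-of-fold scoring left 0.03 to 0.07, which is ordinary regression to the mean. At about 84% positive the fall was 0.02 to 0.06, against 0.005 to 0.011 out-of-fold.
- 200 features, labels driven by stable risk: falls of 0.08 to 0.12 at N = 500, 0.02 to 0.03 at N = 1000 and 0.008 at N = 3000. With 20 features at N = 1000 the fall was 0.004.
- A further set gave falls of 0.03 to 0.33 with 200 features and 0.003 to 0.03 with 50. Whole-cohort shifts stayed within about 0.016, but the t-test rejected in up to about 20-37% of runs in some 200-feature settings. The shift was a small fall at 84% prevalence and a small rise at 10-30%. Cross-fitting brought positives to within 0.01 of zero and the whole cohort to within 0.003.
- The largest whole-cohort shift in any set was +0.024, a rise.

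**6. If training ends before the baseline window.** Here the model is trained on an earlier window and the same patients are scored in two later ones. With a stable trait plus independent noise, the change in positives was -0.005 to +0.005. With features that drift from window to window, a fall of 0.03 to 0.09 remained, part of it regression to the mean.

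**The case against.** Several stronger readings are tempting, and the documents do not support them.

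- **A reader might infer that baseline scores are certainly in-sample.** The text does not say so. That requires training records that cover the baseline window and no hold-out, and the plan is silent on both. The stated aim of evaluating and testing the score may imply a hold-out for accuracy, though it does not say how pilot patients are scored.
- **A reader might infer that the artefact arises wherever the training cut-off lies.** Step 6 shows that it depends on the cut-off and on how notes evolve.
- **A reader might infer that the planned effectiveness t-test is biased towards benefit.** The Statistical Analysis Plan names no misuse-positive subgroup; its only subgroup concerns encounter volume in the Epic usage report. It also does not name the risk score among the t-tested outcomes. Over all LTOT patients the shift is small and can go either way.
- **A reader might take a fall of 0.10 to 0.20 as the expected size.** It reflects assumed feature and patient counts. The 85% misuse figure in Scientific Background is an upper estimate from some studies.

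Two further points stand. The training pool may be wider than the pilot sites, so the degree of overlap is unknown. And this is a pilot whose primary benchmark is provider use of the algorithms.

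What these objections leave intact is the overlap of populations, the absence of any rule separating a patient's training data from that patient's outcome, and a mechanism that is strongest for free-text models with many features. The plan does not say which patients enter the t-test, so an analysis of those with misuse behaviours is neither planned nor excluded.

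**Conclusion.** The concern holds in conditional form. As written, the plan permits in-sample baseline scores to be compared with out-of-sample follow-up scores. If that happens, misuse-positive patients can show a false fall and misuse-negative patients a false rise.

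The size rests on assumptions about patient numbers, feature count and change in the notes: near zero with few or stable features, and about 0.03 to 0.2 or more on the 0-1 score with many text features. The all-LTOT mean shifts by about 0.02 or less in either direction. The main exposure is therefore any analysis of patients with misuse behaviours, with a secondary inflation of false-positive t-tests overall in some many-feature settings.

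**What to change.** Add to Study Design & Methods, Aim 2, and to the Statistical Analysis Plan:

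1. State the training window and the baseline and follow-up scoring windows, and lock the model before any pilot patient is scored.
2. Score each pilot patient at both pre and post with the same model, one not trained on that patient. Use 5- or 10-fold patient-level cross-fitting, or a held-out sample.
3. Keep all of a patient's notes in one fold, select the over-represented terms within training folds only, and report accuracy from the held-out predictions.
4. Give any honest-broker de-identified notes a coded patient link so that they stay in the right fold, or leave them out of the outcome model.
5. State which patients enter the pre/post comparison of the score. Reconcile the number of pilot sites (three in Study Design & Methods, four in Inclusion Criteria), since this decides whose records supply training and outcome data.

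The cost is slightly fewer training patients per model, a few extra fits and, if the de-identified notes are kept, the coded link. No new patient data are needed. The change does not remove ordinary regression to the mean in patients selected for misuse, which any such analysis would have to address separately.

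### The Aim 2 Epic tool report has no count of LTOT encounters, so a PCP's low usage figure is hard to interpret (minor, cheap to improve)

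*Combined protocol and SAP*

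**What the plan says.** The Epic report is set out under Statistical Analysis Plan, Aim 2. Its base is "Monitoring the number of total encounters within the past 2 weeks". Usage is then defined on that base: "For these encounters, obtain data on use of Epic tools designed for the study", the tools being for documentation and for decision and ordering support. The only filter is on visit volume, and it applies to a sub-group: "For sub-group analysis: exclude people with 32 or fewer encounters per week". The unit is the individual PCP: "Analyses will be conducted by provider but de-identified". The SAP does not say whether usage will be shown as a rate or as a count.

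Nothing in that section counts LTOT encounters or LTOT patients. Yet Scientific Background describes the algorithms as guidance for PCPs, "helping them adopt best practices in managing LTOT patients with concerning behaviors", and Inclusion Criteria define the Aim 2 patients as those on LTOT at the pilot sites.

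Elsewhere the plan already works with the relevant population. For the risk score, Study Design & Methods, Aim 2, says: "This analysis will include clinical records of all patients prescribed chronic opioid therapy". Under Study Objectives, the section on integrating the algorithms into the EHR lists prescriptions among the structured data. Neither is tied to the usage report.

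**The concern.** A usage figure is informative when its base is the set of occasions on which the tool could have been used. Total encounters measure workload. If the tools are used mainly at LTOT visits, two PCPs with the same habits but different panels will show different figures, and two with different habits can show the same one. The volume filter does not help, because it selects on how busy a PCP is and not on how many LTOT patients that PCP sees.

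What is at stake is modest but real. This report is the only record-based measure of tool use that the documents describe; the survey and interviews are self-report. The pilot is also meant to rehearse outcome assessment for a later hybrid trial, so a usage measure that is hard to read could be carried forward.

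**Working it through.** The plan states no expected usage, LTOT share or target for this report, so there is no figure to reproduce. What follows is an illustration.

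**Inputs**
- From the documents: a two-week window, a cut-off of 32 encounters per week, and a six-month pilot (26 weeks).
- Assumed: LTOT share of encounters *s* = 1%, 5% or 10%; tools used only at LTOT visits; encounters independent.
- Derived: 2 × 32 = 64, so 65 is the smallest two-week count that averages more than 32 per week. A PCP just above the cut-off has 33 × 26 = 858 encounters in six months.

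**Step 1: the same figure, different uptake.** Usage per encounter *r* = *s* × *u*, where *u* is uptake per LTOT visit, so *u* = *r*/*s*. Take *r* = 0.008, which is 858 × 0.008 = 6.9 expected uses in six months.

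| Assumed share | LTOT encounters in 858 | Implied uptake |
|---|---|---|
| 1% | 8.6 | 0.008/0.01 = 80% |
| 5% | 42.9 | 0.008/0.05 = 16% |
| 10% | 85.8 | 0.008/0.10 = 8% |

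The report shows the same rate and the same count in all three rows. The middle column, which it lacks, is what separates them.

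**Step 2: the same uptake, different figures.** At 80% uptake the three shares give 0.8, 4.0 and 8.0 uses per 100 encounters. If all PCPs had the same share, the figures would follow uptake apart from chance.

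**Step 3: zero counts.** P(no use in *N* encounters) = (1 − *s* × *u*)^*N*. At 80% uptake:
- *N* = 65: 0.992^65 = 59% at a 1% share; 0.96^65 = 7.0% at 5%; 0.92^65 = 0.4% at 10%.
- *N* = 858: 0.992^858 = 0.1% at a 1% share, and essentially zero at 5% and 10%.

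An empty two-week report is thus easy to obtain at a low share, but over the pilot it almost disappears. The mixing in Step 1 does not shrink with more encounters.

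**Step 4: precision with an LTOT denominator.** The Wilson 95% half-width near 50% use is about 27 points with 9 LTOT encounters, 14 with 43 and 10 with 86, if visits are independent. Repeat visits by the same patient widen it: at an assumed design effect of 2, 9 encounters carry the information of 4.5, and the half-width is about 34 points.

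**The case against.** The strongest reply is that the plan never says a PCP's low figure will be read as low uptake. The report is introduced as monitoring, and the SAP states: "Analysis for Aim 2 will be conducted using descriptive statistics and pre/post analysis". It plans no comparison or ranking of PCPs and does not name tool use among the outcomes for its t-tests. All of this stands, and it is why the point is minor.

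A reader might infer more than the documents support, in three ways.
- *That the feasibility result is compromised.* It is not. The benchmark of 80% of PCPs using at least one algorithm comes from the PCP survey, and no decision rule depends on the Epic report.
- *That users will commonly appear as non-users.* The 59% needs one isolated two-week window, the lowest assumed share and the smallest count kept. Over six months the same PCP has a 0.1% chance of showing no use.
- *That the figure carries no information.* Change within one PCP remains readable if the panel mix is stable.

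It can also be said that the spread of 80% to 8% needs a tenfold difference in LTOT share, which the documents do not establish. That is so. But the distortion is proportional: shares of 5% and 10% already give a twofold difference, 16% against 8%.

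One could argue that the LTOT inclusion criterion silently limits the encounters. The SAP's wording is total encounters and states no such limit, and nothing says the tools are confined to LTOT visits either. If a limit is intended, saying so would be most of the fix.

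Lastly, an LTOT denominator is itself imperfect, since it includes LTOT visits at which no concerning behavior arose. That is correct and limits what the fix can claim.

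**Conclusion.** The point holds as a minor one. As written, the report cannot separate how readily a PCP uses the tools from how many LTOT visits that PCP has, so a low figure is hard to interpret. The true size is unknown, because the documents give neither LTOT shares nor their spread across PCPs; the figures above rest on assumed shares, independent encounters and tool use at LTOT visits only. The lasting effect is on descriptive comparison between PCPs with different LTOT shares. The survey benchmark is untouched.

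**What to change.** Keep the two-week total-encounter report for monitoring. Add to the SAP that, for each PCP over the clinic's six-month pilot, the report will give the number of encounters with LTOT patients and the share of them at which a study Epic tool was used, with numerator and denominator shown.

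Identify LTOT patients from EHR prescriptions by extending to the pilot period the chronic-opioid-therapy identification already planned for the risk score, which is retrospective. State the rule used, and make the link before providers are de-identified.

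The cost is a few lines of SAP text and one data link; the documents do not say how easily the Epic report can be linked to a patient list. Two limits should be stated beside the results. Rates will be imprecise for PCPs with few LTOT visits, which is why the counts must be shown. LTOT visits without a concerning behavior stay in the denominator, so the mixing is reduced and not removed.
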